**REM Sleep Behavior Disorders:** 

• REM sleep behavior disorder screening questionnaire (RBDSQ) – is a 10-item, patient self-rating instrument assessing the participant's sleep behavior with short questions that have to be answered by either "yes" or "no". Items 1 to 4 address the frequency and content of dreams and their relationship to nocturnal movements and behavior. Item 5 asks about self-injuries and injuries of the bed partner. Item 6 consists of four sub items assessing nocturnal motor behavior more specifically, e.g., questions about nocturnal vocalization, sudden limb movements, complex movements, or bedding items that fell down. Items 7 and 8 deal with nocturnal awakenings. Item 9 focuses on disturbed sleep in general and item 10 on the presence of any neurological disorder. The maximum total score of the RBDSQ is 13 points.

Bladder function:

• Overactive Bladder Symptom Score (OABSS) is a validated self-administered questionnaire consisting of seven questions on a five-point Likert scale. Five questions are related to urinary urgency and two are related to daytime and nighttime urinary frequency.

Quality of Life

- Parkinson's Disease Questionnaire (PDQ-39): is a reliable, valid, responsive, acceptable, and feasible as the tool for the assessment of quality of life in Parkinson's disease patients. There are 39 questions in the long form Parkinson's Disease Questionnaire, with eight discrete scales: mobility (10 items), activities of daily living (six items), emotional well-being (six items), stigma (four items), social support (three items), cognitions (four items), communication (three items), and bodily discomfort (three items). Patients are asked to think about their health and general well-being and to consider how often in the last month they have experienced certain events. Patients are asked to indicate the frequency of each event by selecting one of five options (Likert Scale): never/occasionally/sometimes/often/always or cannot do at all.
- EuroQoL-5 Dimension-5 level (EQ-5D-5L): consists of two pages-the EEQ-5D-5L descriptive system and the EQ Visual Analogue Scale (EQ VAS). The descriptive system comprises five dimensions: mobility, self-care, usual activities, pain/discomfort, and anxiety/depression. Each dimension has five levels: no problem, slight problems, moderate problems, severe problems, and extreme problems. This is a widely used well validated simple assessment that is comparable across disease populations.
- **1.5** By assessing and comparing the proportion of participants that discontinue the study due to study drug intolerance in the two groups (treatment vs. placebo).
- 2. Overall PD status Change of total MDS UPDRS scores from baseline to the end of 2.5 mg/kg/day visit.
- **3**. Tremor Change of Severity and duration of tremor from baseline to the end of 2.5 mg/kg/day visit: Tremor is measured by the change from baseline to the end of 2.5 mg/kg/day between the two groups:
  - **3.1** Total of scores on items 3.17 and 3.18 in part III of the MDS-UPDRS in the ON state (when anti-PD medication is working). Item 3.17 is rest tremor amplitude. Extremity ratings range from 0: Normal, No tremor to 4: Severe, >10 cm in maximal amplitude. Lip/Jaw ratings are similar but smaller amplitudes. Item 3.18 is constancy of rest tremor: 0 (no tremor) to 4 (present >75% of the exam).
  - **3.2** Item 2.10 in part II of the MDS-UPDRS in the ON state. Item 2.10 is patient's tremor experience: 0 (Not at all. I have no shaking or tremor) to 4 (Shaking or tremor causes problems with most or all activities).
  - **3.3** Total of scores on items 3.15 and 3.16 in part III of the MDS-UPDRS in the ON state. Item 3.15 is postural tremor of the hands: 0: Normal (No tremor) to 4: Severe (Tremor is at least 10 cm in amplitude). Item 3.16 is kinetic tremor of the hands: 0: Normal (No tremor) to 4: Severe (Tremor is at least 10 cm in amplitude).
  - **3.4** Constancy and amplitude of tremor measured by Tremor GUI MATLAB package: Tremor will be measured at clinic and at home (twice a day, two hours after breakfast dose and two hours after dinner dose, for 2 consecutive days after screening visit, three consecutive days before baseline visit and each dose assessment visit). Each time tremor will be measured for

90 seconds. The constancy (percentage of tremor per minutes) and amplitude will be recorded using the package. See Appendix 2. [name] is collaborating on the tremor device.

- **4.** Motor sub-scores Rigidity, bradykinesia, axial, and bulbar sub-scores will also be calculated these are pulled from the motor MDS-UPDRS the change from baseline to the end of 2.5 mg/kg/day visit.
- 5. Emotional control Emotional and behavioral dyscontrol short form score change from baseline to the end of 2.5 mg/kg/day visit.
- 6. Anxiety Anxiety short form score change from baseline to the end of 2.5 mg/kg/day visit.
- 7. Pain Pain intensity short form score change from baseline to the end of 2.5 mg/kg/day visit.
- 8. Sleep sub-study- The primary outcome is the change from baseline to the end of 2.5 mg/kg/day visit on wake after sleep onset (WASO, length of periods of wakefulness occurring after sleep onset), secondary outcomes are changes from baseline to the end of 2.5 mg/kg/day visit on: percentage of total sleep time spent in each sleep stage (N1, N2, N3, and REM), frequency of leg movements during REM, sleep efficiency (proportion of total time in bed spent asleep), total sleep time and the scales of SCOPA-night-time sleep, ISI, DBAS-16, and Pittsburgh Sleep Quality Index.
  - **8.1** Night-time sleep SCOPA-night-time sleep score change from baseline to the end of 2.5 mg/kg/day visit.
  - **8.2** Insomnia Severity Index (ISI): ISI is a verified seven-item self-report questionnaire assessing the nature, severity, and impact of insomnia. A five-point Likert scale is used to rate each item (e.g., 0=no problem; 4=very severe problem), yielding a total score ranging from 0 to 28. The total score is interpreted as follows: absence of insomnia (0-7); sub-threshold insomnia (8-14); moderate insomnia (15-21); and severe insomnia (22-28).
  - **8.3** Modified Dysfunctional Beliefs and Attitudes about Sleep Questionnaire (DBAS-16): A validated self-reported questionnaire designed to identify and assess various sleep/insomnia-related cognitions (e.g., beliefs, attitudes, expectations, appraisals, attributions).
  - **8.4** Pittsburgh Sleep Quality Index: is an effective instrument used to measure the quality and patterns of sleep in adults. It differentiates "poor" from "good" sleep quality by measuring seven areas: subjective sleep quality, sleep latency, sleep duration, habitual sleep efficiency, sleep disturbances, use of sleeping medications, and daytime dysfunction over the last month.
  - 8.5 Home Sleep Monitoring: Polysomnography (PSG) will be performed using a Type II portable, unattended monitor in patients' home. Study subjects will come to clinic to have electrodes and equipment attached by the study coordinator for electroencephalogram (EEG), electro-oculogram (EOG: bilateral), electrocardiogram (EKG), chin electromyogram (EMG), abdominal and thoracic effort belts, oxyhemoglobin saturation (SpO2; finger pulse oximetry; Nonin, Minneapolis, Minnesota), airflow (oral-nasal thermistor), and pressure transducer. Explicit instructions will be reviewed with each subject prior to leaving clinic: directions, timing for completing each questionnaire and initiating sleep recording. A registered polysomnographic technologist (PRSGT) will download and inspect the quality of the recorded signal of the PSG prior to scoring the data. Drs. [name] and [name] are collaborating on conduct of the polysomnograms.
- **9.** Skin evaluation for seborrheic dermatitis in collaboration with Drs. [name] and [name]: Dermatology Quality of Life Index (DLQI) and dermatology photography. DLQI is a dermatology-specific quality of life instrument. It is a simple 10-question validated questionnaire that has been used in over 40 different skin conditions. Dermatology photography (Appendix 3):

take a picture of the central face, as this is the most common area of seborrhea, and send it, with appropriate privacy safeguards, to dermatologists, [name], MD., and [name].

10. Changes of outcome measures 1-7 and 8.1-8.4 from baseline to the end of 1.25 mg/kg/day will be compared between the two groups.

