#### Overview of open label dose-escalation study goals and methodology

We conducted a Phase IIa, open label dose-escalation tolerability study (NCT02818777) in 13 PD patients at the University of Colorado between October 2016 and June 2017, using Epidiolex®. The primary outcome was safety and tolerability, measured by adverse events, changes in examinations, labs, EKGs and percentage of participants that discontinued study drug due to intolerability. The major secondary outcome measure was change in the total of two items on rest tremor in the MDS-UPDRS, and others were measures of most motor and non-motor symptoms that occur in PD. Participants had a screening visit, a baseline visit within the next three weeks, a final dose assessment visit when they have been on the maximal tolerated or the targeted study dose for 10-15 days, and a safety visit 2 weeks later. From the baseline visit, qualified participants took Epidiolex® in a 100 mg per mL sesame oil-based solution orally twice daily. Since somnolence was a reported adverse effect in the pediatric epilepsy population, and Epidiolex® had not been used in persons over age 50, we elected to be cautious and instructed participants not to drive while on study drug.

CBD was started at 5 mg/kg/day and the dose could be increased or decreased by up to 2.5 to 5 mg/kg/day until the study participants reached a maximum targeted dose (20-25 mg/kg/day) or experienced intolerable adverse events (AEs), in which case the dose would be dropped to the last

tolerated dose. Tolerability was assessed via collection of AEs during administration of the standardized phone script by study staff on the third or fifth day of each dose, and the participants were instructed whether or not to change the dose at the end of phone call. Participants filled out home diaries to increase and monitor compliance.

Participants were called at the end of each dose level. During phone calls participants were monitored for AEs, especially excessive daytime sleepiness, symptoms of hepatotoxicity, as well as changes in medical history and concomitant medications. Participants were also called three days after stopping CBD to check for signs of withdrawal. The primary outcome was safety and tolerability of CBD and the secondary and exploratory outcomes examined the effect of CBD on severity and duration of tremor and other conditions that occur in PD.

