## Results

Figure 1 shows the trial profile. Data from all participants that took the study drug were analyzed for safety and tolerability, while only data from those that completed a final dose assessment were analyzed for efficacy. Table 1 shows the baseline clinical and demographic characteristics of safety and efficacy analysis groups.

Figure 1. Open label study profile

[figure not shown]

Table 1. Baseline demographics of the safety and efficacy analysis gro
--

	Safety analysis group (n=13)	Efficacy analysis group (n=10)
Age (years) (mean, SD)	68.1 (6.05)	68.7 (6.65)
Male (n, %)	10 (77%)	8 (80%)

Total MDS UPDRS score (mean, SD)	39.23 (13.32)	43.20 (12.21)
Motor MDS UPDRS score (mean, SD)	22.92 (9.30)	24.70 (8.93)
Disease duration, years (mean, SD)	6.08 (3.99)	6.30 (4.52)
Hoehn & Yahr Scale (mean, SD)	1.73 (0.56)	1.75 (0.59)
MoCA (mean, SD)	28.1 (1.63)	27.9 (1.60)
Levodopa Daily Dose Equivocation (LDDE) (mean, SD)	398.3 (331.00)	443.8 (348.97)

The demographics show that, in general, the participants had an age of onset consistent with the general population of persons with PD and they had early to early-middle stage PD. Generally they had mild bilateral motor symptoms, walked without assistance, had disease for six years, and required a relatively low dose of medication for their motor symptoms. An entry criteria required them to have a relatively significant tremor, but it would be a resting tremor and thus as a general group these participants likely had very little disability. These participants had scored in the normal range on the entry cognitive screening test.

The original protocol was that participants start at 5 mg/kg/day and titrate up to 25 mg/kg/day. Participants were to remain on each dose for three days, until the maximal tolerated dose was reached, and they were to be on that dose for 10-15 days, during which time they came in for an assessment visit.

Due to AEs experienced by our first five enrolled participants and the recommendations of the two PharmDs in our study, the protocol was changed to a slower titration and the maximal targeted dose was reduced from 25 to 20 mg/kg/day, since December 2016. There had been increased AEs and no evidence of additional benefit in the five participants beyond 20 mg/kg/day. Therefore, participants started at 5 mg/kg/day and increased every three to five days by 2.5 to 5 mg/kg/day until reaching a maximal targeted dose (20 mg/kg/day) or experiencing intolerable adverse effects.

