#### Discussion

The primary outcome was safety and tolerability. Generally, the study drug, Epidiolex®, was well tolerated. While adverse effects, mainly somnolence, fatigue, and diarrhea, were frequent, they were generally mild, and there was a relatively low percent of participants, i.e., 23%, that stopped study drug due to intolerability, and no clinically significant abnormalities in testing except for elevated liver enzymes.

Regarding the elevated liver enzymes, GW had seen elevations in their pediatric group, but the pattern was hepatocellular, not cholestatic as in our population. Perhaps age contributed to the difference, since GW had not used Epidiolex® in persons over age 50. In our study liver enzymes were only checked on the highest dose and most of the affected participants were asymptomatic, so it is not clear at what dose the liver enzymes became elevated. [name], Hepatologist, reviewed detailed information on these participants and of all the liver function results in all participants, commented that the changes may represent early liver injury and felt that with close monitoring it was reasonable to move on with the next study. She will be a consultant on the randomized controlled parallel study. The DSMB also reviewed all the data and noted that all changes resolved with cessation of treatment and discussed the possibility the elevations may be related to medication vehicle, i.e., sesame oil. Most participants were talking 10-20 ml per day on the final maximal dose when the testing occurred. The DSMB agreed with continuation of the study with the monitoring plan in this protocol.

Solid conclusions regarding efficacy are not possible from an open label trial, but this study suggested benefit in motor symptoms, night-time sleep, and emotional dyscontrol.

In summary, findings from the open label study suggest that CBD may be efficacious in PD, and that a lower dose may offer the best benefit to risk ratio, compared to the higher dose that GW reports is useful in pediatric epilepsy. Therefore, a lower dose will be used in the randomized controlled parallel study.

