## Dose escalation strategy:

Study product (CBD or placebo) will be started at 1.25 mg/kg/day of CBD (once a day) for four days and then increase to 2.5 mg/kg/day of CBD (twice a day) for 10 (+4) days. Tolerability will be assessed at each dose during each clinic visit. Subjects may take a reduced dose for the duration of the study according to the investigator's medical judgement.

Regarding possible drug interactions, study pharmacists will be provided the calculated dose based on body weight, the list of the subject's medications, and additional relevant clinical information. The final study drug dose will be that recommended by the study pharmacists.

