#### **Participant stopping rules:**

- If participant cannot tolerate the study drug at any dose level
- if participant develops a CTCAE criteria grade 3 or 4 adverse event per that the Investigator determines is related the study drug
- Pregnancy or breast-feeding
- Requested by participant to terminate treatment
- Failure by the participant to attend consecutive study visits
- Participant is at significant risk of failing to comply with the provisions of the protocol as to cause harm to self or seriously interfere with the validity of the study results
- At the discretion of the IRB, Food and Drug Administration (FDA)

If a participant is withdrawn from the study, all efforts will be made to complete the early termination visit that includes efficacy assessments and safety follow-up. In addition, women of childbearing potential will have a post-study pregnancy test performed at the early termination visit.

Withdrawals and the reason for withdrawal will be tabulated by treatment group. The number and percentage of participants who complete the study will be summarized by treatment group. The number and percentage of participants who withdraw from the study will be tabulated by original treatment group and last treatment taken at time of withdrawal. Study medication discontinuations will be summarized in a similar fashion.

Participants will be advised that they are free to withdraw from the study at any time. Reasons that participants may be withdrawn from the study include the following:

Participant discontinued study medication and wishes to withdraw.

Participant consent is withdrawn.

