- 2. Vital signs, orthostatic blood pressures, physical exam, EKG, and labs (hematology, complete metabolic profile, urinalysis) will be done during study visits. For vital signs and labs, data will be analyzed as a simple two-period trial. Means and confidence intervals will be presented pre and post treatment by treatment group, and for the change scores by treatment group. A two independent sample T-test will compare the means of the change scores between the treatment groups. More complex situations can be analyzed with longitudinal regression models.
- 3. Standardized assessment tools (MoCA, Cognition assessment battery, Anxiety short form, NPI, SCOPA-Sleep, ISI, DBAS-16, Pittsburgh Sleep Quality Index, RBDSQ, QUIP-RS, C-SSRS, Depression short form, Emotional Behavioral dyscontrol short form, Fatigue severity scale, MDS UPDRS, UDysRS, Pain Intensity 3a short form and Pain Intensity 4a short form, IRLS, PDQ-39 and EQ-5D-5L) and lab tests, the data will be analyzed as a simple two-period trial. Means and confidence intervals will be presented pre and post treatment by treatment group and for the change scores by treatment. A two independent sample T-test will compare the means of the change scores between the treatment groups. More complex situations can be analyzed with longitudinal regression models.
- 4. Proportion of participants who drop out of the study due to study drug intolerance. Analysis (proportions of participants who drop out of the study due to study drug intolerance in the two treatment groups) will be mostly descriptive, and proportions and confidence intervals will be calculated. Proportion differences between groups can be compared with the standard test.

**Exploratory Outcome Measures:** The efficacy of CBD on cognition, psychosis, sleep, daytime sleepiness, mood, fatigue, pain, impulsivity, other motor and non-motor PD signs, restless legs syndrome, REM sleep behavior disorder, quality of life, and plasma levels of cytokine are evaluated using the aforementioned assessment tools. The change from baseline to end of 2.5 mg/kg/day is compared.

Exploratory analyses: To study the efficacy of CBD on cognition, anxiety, psychosis, sleep, daytime sleepiness, mood, fatigue, pain, impulsivity, other motor and non-motor PD signs, restless legs syndrome, REM sleep behavior disorder, plasma levels of cytokine, and seborrheic dermatitis.

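### The named tolerability proportion counts leaving the study, not stopping the drug, for intolerance, so it can understate intolerance by an amount the plan leaves open

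*Combined protocol and SAP*

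**What the plan says.** Section IV.A, Secondary Outcome Measures, item 1.5, assesses tolerability "By assessing and comparing the proportion of participants that discontinue the study due to study drug intolerance in the two groups". Section IV.F, safety and tolerability item 4, carries the same definition into the analysis: "Proportion of participants who drop out of the study due to study drug intolerance". That analysis is to be mostly descriptive, with proportions and confidence intervals, and the group difference may be tested.

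Three other places bear on what is counted:

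- **Section C.1, Dose escalation strategy:** "Subjects may take a reduced dose for the duration of the study according to the investigator's medical judgement".
- **Section C.1, Assessment of tolerability of each dose level:** a grade 2 event leads to a dose reduction, and a related grade 3 or 4 event leads to permanent cessation of study drug. Neither rule says that the participant leaves the study.
- **Section C.5, Participant stopping rules:** withdrawals and their reasons are tabulated by treatment group, and then "Study medication discontinuations will be summarized in a similar fashion". The section also gives, as one reason for withdrawal, having stopped the medication and wanting to leave. Stopping the medication is therefore not by itself a withdrawal.

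The open-label stage described in Section III used a drug-based measure, the "percentage of participants that discontinued study drug due to intolerability".

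**The concern.** Safety and tolerability form hypothesis 2 and open the secondary aim. The question is whether people with Parkinson's disease can stay on the drug, but outcome 1.5 records whether they stay in the trial. A participant whose drug is stopped for intolerance and who still attends later assessments would not be counted. Nor would one kept on a reduced dose because the target was not tolerated.

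Section IV.F follows the intention-to-treat concept, which favours continuing to assess participants who stop the drug. The more successfully the site does this, the lower the named intolerance proportion becomes, with no change in how well the drug is tolerated. Item 4 is also the only discontinuation proportion for which the plan provides a between-arm comparison.

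**Working it through.** **1. The open-label figure.** The Section III Discussion says that "there was a relatively low percent of participants, i.e., 23%, that stopped study drug due to intolerability". Table 1 gives 13 participants in the safety group. The count is not stated in the text available, but 3 is the only whole number out of 13 that gives 23%: 2/13 = 15.4%, 3/13 = 23.1%, 4/13 = 30.8%. The figure reproduces. Its exact (Clopper-Pearson) 95% confidence interval is 5.0% to 53.8%.

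**2. Direction of the error.** Anyone who leaves the study because of drug intolerance has also stopped the drug. Those counted by outcome 1.5 are therefore a subset of those who stop the drug for intolerance. Let p be the true proportion stopping the drug for intolerance in an arm, and f the share of them who stay in the study. Then

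proportion shown = p × (1 − f).

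This equals p when f = 0 and is below p otherwise. If f is the same in both arms, the between-arm difference shrinks by the same factor (1 − f). If f differs between arms, the difference can move either way.

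**3. Illustrative size.** The documents give no value for f and no rate of stopping for this regimen. Assume p = 3/13 = 23.1% on CBD and let f run over its whole range. Counts are shown for 30 per arm (the completion goal in C.1) and for 37 per arm (75 recruited, 1:1, 75/2 = 37.5, rounded down).

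| Share of drug-stoppers who stay in the study (f) | Outcome 1.5 shows | Count out of 30 | Count out of 37 |
|---|---|---|---|
| 0% | 23.1% | 6.9 | 8.5 |
| 25% | 17.3% | 5.2 | 6.4 |
| 50% | 11.5% | 3.5 | 4.3 |
| 75% | 5.8% | 1.7 | 2.1 |
| 100% | 0% | 0 | 0 |

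For example, at f = 50%: 0.231 × 0.5 = 0.115, and 37 × 0.115 = 4.3. The understatement ranges from 0 to 23.1 percentage points under this assumed p.

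**4. Can f be read from the documents?** No. The tolerability rules in C.1 speak of stopping the drug. C.5 lists inability to tolerate any dose, and a related grade 3 or 4 event, as participant stopping rules. It then goes directly to study withdrawal and an early termination visit. Yet the same section separates medication discontinuation from withdrawal. Both readings are open, and with them any f from 0 to 1.

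**The case against.** The strongest reply is that the error may not exist. C.5 places intolerance and related grade 3 or 4 events among the rules that stop a participant, next to the withdrawal text. No procedure is described for someone who is off drug but continues the visit schedule, and Visits 3 and 4 are built around taking a dose on arrival. If every stop for intolerance becomes a withdrawal, outcome 1.5 counts it. This stands: a reader might infer that the outcome does understate intolerance, but the documents show only that it can.

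Second, C.5 already plans a summary of drug discontinuations by arm, and outcome 1.1 compares study-related adverse events at each dose level. Tolerability does not rest on 1.5 alone, and an event that leads to a dose reduction would appear under 1.1 if judged study-related. This also stands and limits the harm. However, the C.5 summary is a disposition table. It is not the named outcome, is not restricted to intolerance, and has no planned comparison. Outcome 1.1 counts events, not whether participants could stay on the drug.

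Third, a reader might infer that the result cannot be compared with the open-label 23% because dose reductions go uncounted. The documents do not support that. The open-label stage also lowered the dose for intolerable events, and its 23% counted only those who stopped. No comparison with that figure is planned. It comes from 13 open-label participants taking a different product at a target of 20 to 25 mg/kg/day, against 2.5 mg/kg/day here. It is a weak benchmark under any definition.

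**Conclusion.** The point holds as a defect of definition. Outcome 1.5 and analysis item 4 name an event, leaving the study, that need not coincide with the event of interest, stopping the drug because it is not tolerated. The within-arm proportion can understate intolerance and cannot overstate it by this route.

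The size is not established. It is zero if every stop for intolerance is a withdrawal, and at most the full drug-stop rate if none is. The 23% to 0% range rests on two assumptions: a stopping rate borrowed from a small open-label stage at a much higher dose, which the protocol expects this regimen to improve on, and an unknown share who stay in the study. Confidence is high on the wording and low on the magnitude. This is an inexpensive improvement to a secondary outcome, and the primary analysis and sample size do not depend on it.

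**What to change.** In Section IV.A item 1.5 and Section IV.F item 4, define the outcome as *the proportion of participants who permanently discontinue study drug due to study drug intolerance, whether or not they remain in the study*. Compare that proportion between arms as item 4 already allows. Keep study withdrawal, with reasons, as the separate tabulation in C.5. Limiting the definition to drug intolerance keeps out stops for unrelated events.

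The C.1 tolerability rules and C.5 should be reconciled so that it is clear whether a stop for intolerance also ends participation. The revised outcome gives the same count either way.

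Optionally, report descriptively by arm the participants below the target dose at Visit 4 because of study drug intolerance, as a separate line. This requires the reason for the reduced dose to be recorded. The diary captures the dose and events, but the plan does not say that it captures the reason.

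The cost is a change of wording in two places. The discontinuations are already to be summarized under C.5, though the reason for stopping the drug must be recorded for each case. The downside is that the reported intolerance figure may be higher.
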